STUDY PROTOCOL
May 1, 2017

Project Title: Integrating Safer Conception Counseling to Transform HIV Family Planning Services

NCT03167879

Registered on clinicaltrials.gov on 5/23/17

STUDY PROTOCOL

Overview. This 3-arm, cluster RCT will compare two models for implementing a comprehensive FP program that integrates SCC within current FP services in HIV clinics—an up to 6-session, multi-component, structured SCC intervention (SCC1), and a workshop to train FP providers on use of SCC guidelines (SCC2)—versus existing FP services (usual care). Both SCC1 and SCC2 will use routine screening for fertility desires and a workshop for training FP nurses to implement SCC, but SCC1 is differentiated by its use of a structured counseling SCC protocol and manual (as opposed to the clinical acumen of the trained FP nurses), and inclusion of client outreach and ongoing supervision support. Each arm will be implemented at 2 sites (6 sites in total) and each site will enroll 65 clients (total n=390) with serodiscordant partners who have childbearing desires at recruitment. Participants will be surveyed at baseline, months 6 and 12, and post-pregnancy for those who become pregnant prior to month 12. The primary outcome is correct use of SCM or contraception (depending on desired pregnancy status following SCC consult); secondary outcomes are pregnancy status, PMTCT use (if pregnant), partner seroconversion, and condom use. A cost-effectiveness analysis will also compare the 3 arms to inform policy and practice recommendations for settings of various resource levels.

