IMB asserts that **information** about the transmission risks of childbearing and how SCM and PMTCT limit these risks is a prerequisite but insufficient to ensure use of SCM/PMTCT or contraception, and that motivation and behavioral skills to use these methods are critical. **Motivation** is fed by beliefs that SCM and PMTCT greatly reduce transmission risks and contraception prevents unplanned pregnancy, and confidence in being able to use these methods. **Behavioral skills** such as calculating the fertile days of a woman's ovulation cycle, using a syringe to manually inseminate the woman, and negotiate condom and contraception use with one's partner, are key to SCM and contraception use. The **sociocultural context** for childbearing in PLHA affects each of the IMB components: HIV+ peers, providers, partners, family and community are sources of information (or misconceptions), attitudes, beliefs, and support (or stigmatization) for childbearing and use of contraception, SCM and PMTCT, all of which affect knowledge, motivation, and self-efficacy for use of these methods. Stigmatization of childbearing by providers,^{17,26,33} family and community²⁷ contributes to poor provider-patient communication about fertility needs and greatly impedes clients receiving needed SCC.

To address each eIMB construct, the multi-component intervention consists of: 1) training expert clients and village health team workers (VHTs) to engage in **client and community outreach and education** about the

childbearing needs of PLHA and availability of comprehensive FP services including SCC to promote SCM use and reduce childbearing stigma; 2) **provider training and supervision** to sensitize providers to childbearing needs of PLHA, reduce provider stigma of childbearing, and develop and sustain their skills and self-efficacy for providing SCC; 3) **routine screening of childbearing desires** to facilitate timely identification of clients in need of SCC or contraceptives; and 4) **structured, manualized SCC sessions** administered by FP nurses to promote informed childbearing decisions and use of SCM, PMTCT and contraception. The intervention will be incorporated into the clinic's model of care and applied to all clients, not only research participants.

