Routinely collected clinic data will be used to analyze FP services in the overall clinic population to examine clinic capacity and fidelity to the intervention. The triage book and childbearing screening item (in SCC1/SCC2 sites) will be used to determine: (a) # who do not want children and % receiving contraception services, and (b) # reporting childbearing desires. FP registries will indicate # new clients receiving FP services (not seen by FP in past year), and % of FP recipients using dual contraception. These will be tracked longitudinally to assess intervention effects on clinic level FP services. % of clients receiving FP referrals after triage will be compared across all 3 arms using research cohort data, since childbearing screening is not used at the usual care site.

Research Participants. The assigned FP programs at each study site will be implemented clinic-wide for all clinic clients, but the 66 study clients enrolled at each site will meet the following **eligibility criteria**:

1. Adults of reproductive age (men age 18-60; women age 18-45).
2. Considering childbearing with their spouse/partner. This will be determined via the triage screening item.
3. Reports having disclosed HIV status to partner. TASO counselors provide clients with assisted disclosure services to help them disclose to partners. Therefore, interested clients who have not yet disclosed their HIV status to their partner will be assisted to do so if they wish, after which they can be considered for enrollment.
4. Partner is HIV-negative. All couples can benefit from SCC and FP, but we focus on discordant couples due to the heightened value of SCC for reducing horizontal HIV transmission. We will use a rapid HIV test to confirm partner's status, and offer the option of a home-based test (a service offered by TASO) if necessary. Confirming the partner's status enables us to accurately assess intervention effects on seroconversion.

ART use is not an eligibility criterion, but SCC will be used to advise and support clients to start and adhere to ART before trying to conceive with SCM. TASO provides ART to all clients in serodiscordant relationships.

Note that only the HIV+ client will enroll in the study and participate in the survey research, not their partners.

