Recruitment. We will enroll 3-4 clients per month over 18 months at each site, which is feasible as >20 clients met this eligibility criteria in each recruitment month in our pilots. Recruitment will be stratified by sex to ensure a 50/50 gender balance, which will better enable us to examine intervention effects on partner seroconversion

and to gain the perspective of both male and female clients regarding fertility. We could enroll the sample more quickly, but the long enrollment period ensures we can recruit the target number of men, and enables us to have our 3 site coordinators manage three sites each (min. 1 day per week at each clinic) to limit personnel costs. Clients at the SCC1 and SCC2 sites who report at triage that they desire to have a child with a negative or unknown HIV status partner will be referred by triage to the site coordinator for screening. Screening (incl. partner HIV testing) and baseline survey will be completed prior to the initial SCC consultation. At the usual care site, the childbearing screening item will be included at triage only during the days of recruitment, which will be used to identify potential participants who will then be referred to the site coordinator for the same screening conducted at the intervention sites; the data from the screening item will not be placed in the client's chart or given to the FP nurse, as this screening is not part of usual care. Clients who decline to bring their partner in for HIV testing (but are otherwise eligible) and thus do not participate, will be asked to provide basic sociodemographic and partner characteristics in order to assess how they differ from the enrolled clients.

Data Collection

Assessment schedule: The baseline assessment will be done by the site coordinator once eligibility is confirmed, followed by assessments at months 6, 12, and post-pregnancy (if pregnancy occurs prior to month 12). To minimize attrition we will collect contact info (phone numbers and maps of homes), including contact information for family or friends who have frequent contact with the client. Clinic staff will also be able to help us track clients that we have difficulty reaching. In our current study we achieved 94% retention at Month 12.

Participant Compensation: Participants will receive 20,000 Ush (~\$6 USD) at each assessment.

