Data analysis: Our primary analysis will be to compare the combined intervention arms (SCC1 & SCC2) against the usual care control to assess the effects of integrating SCC into FP services, and then compare the outcomes between the two intervention arms to determine whether the more intensive SCC1 shows a larger effect than the less intensive SCC2. The primary outcome-- correct use of contraception/SCM (depending on pregnancy intention)-- will be represented as a binary variable as defined in D.2.3.5, but we will also explore a categorical or continuous outcome derived from frequency of correct use throughout the study. Secondary outcomes to be investigated are pregnancy status, PMTCT use, consistent condom use, and seroconversion of partner. We will use an intent-to-treat approach in the primary analyses; secondary analyses will use only study completers. Participants remain in the study and analysis regardless if their relationship status changes during the study. Attrition weights will be used to account for dropouts, and analyses will incorporate design effects from this weighting in the calculation of standard errors and tests of significance. We will account for clustering, and with only 9 clusters/clinics we will conduct individual level analysis. Regression methods can directly model correlations among units in a cluster (random effects or multilevel models) or more simply adjust standard errors for clustering (GEE, robust standard errors), but these approaches are not reliable with so few

clusters,⁷⁵ so we'll use standard regression methods, but rather than attempt to estimate ICC directly, we will explore the sensitivity of significance levels using a range of plausible ICCs values for the outcomes.

Aim 1: Assess intervention effect on contraception/SCM use: *Hypothesis: Both SCC1 and SCC2 will be superior to usual care, and SCC1 will be superior to SCC2 regarding the primary outcomes.* We'll use logistic regression to compare rates of contraception or SCM use (depending on pregnancy intention) in the SCC1 and SCC2 interventions compared to the control condition, and investigate differences between SCC1 and SCC2 in a separate regression. The models will include covariates to adjust for baseline variables (e.g., childbearing stigma, age, sex) that may differ at baseline and to increase precision of the estimates.

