Aim 4: Cost-effectiveness analysis. We will track all costs associated with implementing SCC1 and SCC2 beyond those of existing FP services (the costs of which we will also measure), such as labor costs associated with SCC sessions and consults with FP nurses, supervision of the FP nurses (in SCC1), contraceptives and SCM client kits, and cost of intervention materials (posters, SCM instructional videos). Labor costs are based on clinic-specific data, external sources, and our own documentation (e.g., # and length of SCC sessions, FP consults, supervision meetings). Fixed costs will be allocated to the intervention as the fraction of time the premises are used for the intervention (e.g., SCC sessions). Training materials and supplies will be costed at purchase prices. Development costs such as personnel costs for the SCC training workshop will be differentiated from ongoing operational costs, but will exclude research costs (e.g., surveys). We will also evaluate potential efficiencies in operational costs (SCC sessions and ongoing supervision) over time and differentiate between the fixed costs of the intervention and the marginal cost of adding an additional client to inform generalizability to other settings. The analysis will be performed from the clinic perspective as we cannot accurately incorporate costs incurred by the client (e.g., lost earnings on clinic visit days), but the coordinator will track the number and duration of SCC sessions, and the survey will assess transportation and other client costs. We will assess whether the intervention is cost-effective by assessing the cost-effectiveness ratio (CER), defined by the difference in per-capita cost of the two intervention models relative to the control. We will assess average overall and marginal cost per achieved pregnancy (without partner seroconversion) or prevented pregnancy (depending on the patient's desired pregnancy status) and compare those to published values such as Shade et al.⁸⁰ We will estimate confidence intervals for our CERs using bootstrap methods.⁸¹

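### Aim 4 names no bootstrap unit, and with two clinics per arm neither choice gives a reliable interval; the population behind per-capita cost is also undefined

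*Combined protocol and SAP*

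**What the plan says.** In the Data Analysis Plan, Aim 4 will track the costs of implementing SCC1 and SCC2 beyond those of existing family planning services. The CER is "defined by the difference in per-capita cost of the two intervention models relative to the control". The paragraph then turns to average and marginal cost per achieved pregnancy without partner seroconversion, or per prevented pregnancy. On uncertainty there is one sentence: "We will estimate confidence intervals for our CERs using bootstrap methods". The resampling unit, the type of interval and the handling of clinics are not given.

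Under Arm 1 the plan states: "The intervention will be incorporated into the clinic's model of care and applied to all clients, not only research participants". The Research Participants section says the same of the assigned programme at every site. Surveys and mandatory partner HIV testing apply to enrolled clients only.

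The Overview gives two clinics per arm, six in all, with 65 clients each. The Research Participants section instead refers to "the 66 study clients enrolled at each site", and the Data analysis paragraph says "with only 9 clusters/clinics we will conduct individual level analysis". That paragraph also judges random-effects, GEE and robust-standard-error methods unreliable with so few clusters. In their place it plans a sensitivity analysis over plausible ICCs for the outcome tests. Aim 4 has no counterpart.

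**The concern.** Clinics were randomised, and much of the programme's cost (training, supervision, outreach, materials) arises at clinic level. A bootstrap that does not reproduce clinic-to-clinic variation gives intervals that are too narrow. One that resamples two clinics per arm has almost nothing to resample.

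The CER also needs costs and effects from the same people. The programme serves everyone at the clinic, while the seroconversion-free pregnancy outcome is reliably known only for enrolled clients. Without a stated denominator and a rule for sharing common costs, two analysts could follow Aim 4 and reach quite different ratios.

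This matters because the Overview says the analysis is to inform policy and practice. The Arm 3 text says the clinic operator will decide on adoption after seeing efficacy and cost-effectiveness data.

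**Working it through.** **Plan's own figure.** Aim 4 states no ratio, interval or precision, so there is none to reproduce. The Overview total agrees: 6 x 65 = 390.

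**Inputs from the documents.** 2 clinics per arm and 65 clients per clinic (Overview). ICC 0.01, 10% attrition and a 15% usual-care rate (Power analysis). More than 20 eligible clients a month in the pilots and 18 months of enrolment (Recruitment).

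**Assumed for the simulations.** A 35% intervention rate, a between-client cost CV of 0.5, a between-clinic cost CV of 0 to 0.2, and a second ICC of 0.05. The 15% is the primary-outcome rate, used as a stand-in because the documents give no pregnancy rate. There were 1,500 simulated two-arm trials with 58 clients per clinic and 500 resamples each, using percentile intervals.

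**1. Resampling clinics.** Distinct resamples per arm = C(2k-1, k). With k = 2 this is C(3,2) = 3 (AA, AB, BB, with probabilities 1/4, 1/2, 1/4), so 3 x 3 = 9 for a two-arm contrast. Each extreme difference has probability 1/4 x 1/4 = 1/16 = 6.25%. That exceeds 2.5%, so the 95% percentile interval simply runs from minimum to maximum.

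Take clinic means as normal with common SD s. The error of the estimated difference is s|Z|. The half-width is s(|Z1| + |Z2|)/√2 = s max(|W1|, |W2|), where W1 and W2 are independent standard normals. The interval misses only when |Z| is the largest of three exchangeable values, which has probability 1/3. Coverage is therefore 2/3, about 67%. Simulation gives 65-68% for the effect difference, 58-60% for the cost difference and 66-75% for the ratio.

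**2. Resampling clients.** Analysed per clinic: 65 x 0.9 = 58.5. Design effect = 1 + (58.5 - 1) x ICC. Coverage = 2Φ(1.96/√deff) - 1.

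| ICC | Design effect | True SE / bootstrap SE | Effect-difference coverage, formula | Effect-difference coverage, simulated | Ratio coverage, simulated |
|---|---|---|---|---|---|
| 0.01 | 1.575 | 1.25 | 88% | 86-88% | 89-93% |
| 0.05 | 3.875 | 1.97 | 68% | 67% | 80-83% |

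For the cost difference at ICC 0.01, coverage is 94%, 70% and 46% at between-clinic cost CVs of 0, 0.1 and 0.2. The ratio and cost figures move with the assumed costs, so they are indicative only.

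**3. If there are nine clinics.** With three per arm, C(5,3) = 10 resamples per arm. Clinic-bootstrap coverage of the ratio is about 79-87%, still short of 95%.

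**4. Ratio near zero effect.** As the resampled effect passes through zero the ratio jumps between very large positive and very large negative values. A negative ratio can mean dearer and worse, or cheaper and better. Ranking replicates to read off percentiles then has no meaning. The documents give no basis for saying how often this would happen.

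**5. Denominator.** If the pilot rate held at each site, 20 x 18 = 360 eligible clients per clinic over enrolment, against 65 enrolled. 360/65 = 5.5. This is the overstatement of shared cost per client if those costs were divided by 65 rather than by those eligible.

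**The case against.** A reader might infer that Aim 4 divides clinic-wide costs by the 65 enrolled clients. The documents do not say so. The Arm 2 section logs sessions attended by participants. Aim 4 tracks session number and duration, separates development from operational costs, and separates fixed cost from the marginal cost of one more client. A matched per-client cost is therefore possible under the plan, though nothing requires it. Fixed costs are allocated to the intervention by premises time, which does not divide them between enrolled and other clients.

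A reader might also scale the mismatch up to the 6,000-8,000 clients of each clinic. That is unsupported. It counts people outside reproductive age or without childbearing desires, and session labour and kits rise with the number served, so only shared costs are exposed. Even the 5.5 is conditional: the pilot rate is not stated per clinic.

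On the interval, the plan never proposes resampling clinics, and the Data analysis paragraph commits to individual-level analysis, so client resampling is the more natural reading. Under it, the ratio's shortfall at ICC 0.01 is modest in these simulations, and the severe cost-difference figures need assumed clinic cost variation. Nor is a percentile interval specified. These points stand and limit the claim.

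One might use the 4.5-point difference in the Power analysis to predict how often resampled effects fall below zero. That figure concerns correct use of contraception or safer conception methods, whereas Aim 4's effect is pregnancies achieved or prevented, so no such percentage is given here.

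Finally, moving to net benefit does not by itself cure clustering. With client resampling at ICC 0.01, simulated coverage on that scale is 83-87%. Two clinics per arm cannot estimate a clinic variance component on any scale.

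**Conclusion.** The interval problem holds. Aim 4 as written gives intervals that are too narrow whenever clinics differ. Coverage of the effect difference is about 67% if clinics are resampled (normal clinic means, equal variance) and about 88% if clients are resampled at the plan's own ICC. Ratio coverage under client resampling, 89-93%, rests on assumed costs and an assumed 20-point effect (35% against 15%), and falls with a larger ICC. The plan recognises the few-cluster difficulty for its outcome tests but does not carry its remedy into Aim 4.

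The cost side holds only as a gap in definition. The per-capita population and the sharing of training, supervision, outreach and materials are unspecified, so a mismatch is possible rather than planned. The 5.5-fold figure is its size under one stated assumption, and only for shared costs. The documents do not support a claim that the ratio will be badly wrong.

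**What to change.** - **One population for costs and effects.** Spread shared clinic-wide costs over all clients served, then add each enrolled client's own session costs from the logs. State the head-count source and the sharing rule.
- **Show the clinics.** Report costs and effects for each clinic. Reconcile six with nine clinics, and 65 with 66 clients per site.
- **Replace the single bootstrap ratio interval.** Use incremental net benefit over a range of values per outcome, with acceptability curves. Show uncertainty over a stated range of ICC and between-clinic cost variation, extending to Aim 4 the ICC sensitivity already planned for the outcomes.

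The cost is SAP wording, some health-economics analysis and some head-count work: the family planning registries count new family planning clients, not recipients of safer conception counselling. The range of values per outcome must also be chosen, since the documents give none. Intervals will be wider.
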